#### 8-Week Dietary Intervention

Participants will be provided all meals that are prepared by the PBRC metabolic kitchen (5-day meal rotation) and given both verbal and written instructions as to the consumption of the

food. On weekdays, at least one meal (i.e. breakfast, lunch, or dinner) will be consumed at PBRC 3 times per week, (excluding holidays), whereas the other weekday meals will be packaged for takeout. In addition, alcohol, weekend, and holiday meals will be packaged for takeout. Participants' energy requirements will be determined from their estimated resting metabolic rate (RMR), calculated via the Mifflin-St. Jeor formula, with an activity factor of 1.5. The energy requirements will then be multiplied by 0.70 so that all participants will restrict energy needs by 30% compared to weight maintenance. Each group (control and ethanol) will have the same 30% reduction in calories and will consume the same percentage of each traditional macronutrient (20% protein, 50% carbohydrate, and 30% fat). The ethanol group will consume a 30% energy restriction diet that will also include ~2.5 standard drinks, or 35 grams of ethanol, administered as 80-proof distilled spirits (e.g. 80 proof gin, rum, vodka, whiskey, or tequila). In the United States, one "standard" drink contains roughly 14 grams of pure alcohol. Caloric differences between the spirits will be accounted for by being administered on specific days of the meal rotation so that the appropriate mixers are provided. The remaining calories (Mifflin-St. Jeor formula, with an activity factor of 1.5 multiplied by 0.70 minus the ~240 kcals from ethanol) will be consumed as 20% protein, 50% carbohydrate, and 30% fat. The control group will consume these ~240 kcal as included in the aforementioned macronutrient percentages (20% protein, 50% carbohydrate, and 30% fat).

Participants will be asked to have an in-clinic check in once per week when coming for their in-house meal. At this check a metabolic weight will be obtained, adverse events and changes in medication will also be assessed. The ethanol group will be also be administered the alcohol-related questionnaires.

#### Instructions for Alcohol Consumption

The alcohol will be treated with additional oversight and will be purchased, logged, handled, and dispensed by the PBRC pharmacist. Women randomized to the ethanol group will be provided detailed verbal and written instructions regarding the consumption of alcohol. Participants will be provided with a list of the specific types of alcohols that are permitted. Measured doses of alcohol will be prepared by the PBRC pharmacist. Sealed, individual bottles (~7) of alcohol will be dispensed to the participant once per week (Monday; excluding holidays) through PBRC clinic. Each bottle will contain a pre-measured dose of alcohol, and participants will drink one bottle per day of the week. The subject will be instructed to consume the alcohol over the course of a couple hours at home (not strictly before bedtime) so as not to interfere with important daily tasks and to avoid periods where it is necessary to drive. She will be given general information about alcohol and informed of the effects of its use on the body, including impaired coordination, judgment, alertness, and diminished quality of sleep. The participants will be warned of the risks associated with performing daily activities and operating vehicles or other machinery after alcohol ingestion. Subjects will also be provided information about the warning signs of alcohol dependency.

#### Dietary and Alcohol Compliance

Compliance with consuming the study meals and alcohol will be monitored. The consumption of select meals and the ingestion of all alcoholic drinks will be monitored by study staff via video technology (e.g. Skype, cellular phone device) designed to quantify dietary compliance. A daily diary will be completed by the women each day to document the time and amount of the study alcohol consumption. This diary will be returned at the Monday clinic visit (excluding holidays). Participants will also complete a food and alcohol consumption log at the daily study visits. Subjects will be instructed to report if any additional food, beverages, and alcoholic drinks were consumed. Subjects who are under-compliant (<85%) or over-compliant (>100%) will be counseled by study staff on the importance of compliance. Repeated (i.e. >2 events) under- or over-compliance will result in the participant being dropped from the study.

Body weight will be monitored weekly during the intervention. All collected data will be documented. Collectively, these methods will be implemented to enforce dietary compliance during the intervention.

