## **II. STUDY RATIONALE AND OBJECTIVES**

This is a novel pilot study to examine, for the first time, the effects of ethanol consumption on fat distribution and testosterone during weight loss in a RCT. Findings from this study would provide insight into an interesting and unanswered question -- does routine alcohol intake exert unfavorable health effects despite the expected beneficial outcomes of caloric restriction and weight loss? This research may provide new knowledge of the metabolic outcomes resulting from alcohol intake and pathways that may be involved leading to potential new therapeutic targets of treatment.

The *objective* of the proposed study is to enroll women with obesity that will undergo a controlled, energy restricted feeding intervention to test the effects of chronic ethanol consumption on adipose distribution and circulating testosterone during weight loss. Women will be randomized to an ethanol-free control group or an ethanol-consuming group, and all will consume 30% energy-restricted diets.

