### **b. Inclusion criteria**

- Pre-menopausal women only
- 21-40 years of age
- BMI 27-50 kg/m^2 (+ 0.5 will be accepted)
- Must practice and be willing to continue to practice appropriate birth control (defined as a method which results in a low failure rate, i.e., less than 1% per year, when used consistently and correctly, such as double barrier methods [male condom with spermicide, with or without cervical cap or diaphragm], implants, intrauterine contraceptive devices, tubal ligation (surgically sterile), abstinence, or in an established relationship with a vasectomized or same sex partner) during the entire duration of the study

- Must be willing to adhere to all study procedures, including consumption of all study foods and beverages and attendance at all study visits
- Must be willing to eat at least one meal at PBRC 3 times per week on weekdays (excluding holidays)
- Must be willing to consume alcohol
- Must be willing to abstain from alcohol for 8-weeks if randomized to non-alcohol control group.
- Must be a daily, or almost daily drinker, defined as typically consuming at least 8 drinks per week, but no more than 4 per day
- Must be willing to undergo an overnight alcohol test (at home) of ethanol at the proposed dose before enrollment in the study
- Must have access to a device that can be used for video monitoring of compliance (i.e. Skype)
- Must be willing to have your blood stored for future research

c. Exclusion criteria

- Non-drinkers of alcohol
- Habitual binge drinkers, as defined by the consumption of  $\geq 4$  standard drinks per day or  $\geq 28$  drinks per week.
- Self-reported alcoholics or a history of alcoholism
- Have a 1st degree relative with alcoholism
- Any attendance or inpatient stay for alcohol or drug treatment
- Display any characteristics of current or future substance abuse disorders
- Presence of any psychiatric, behavioral, or medical disorder that, in the opinion of the PIs, Co-I, or MI, may interfere with study participation, the ability to adhere to the protocol, or has the potential for increased substance abuse
- Prescription medications that interact with alcohol intake
- Abnormal screening laboratory safety tests
- Smokers
- Diagnosis of Type 1 or 2 diabetes mellitus, cancer, or major organ disease
- Serious digestive disorders
- Conditions that affect metabolism or body weight (i.e. uncontrolled thyroid conditions, bariatric surgery, pregnancy, breastfeeding)

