participants will be screened and excluded for the presences of diagnosable mood and/ or personality disorders that would interfere with the ability to adhere to protocol. Structured Clinical Interviews (SCID-5 and SCID-5 PD) are semi structured guides to interview that enhance and standardize diagnosis or evaluation of various psychological disorders. The SCID 5 evaluates DSM 5 diagnoses, including mood disorders, psychotic symptoms, psychotic disorders substance use, etc.). The SCID 5 PD is an evaluation of 10 different personality disorders including: Avoidant Personality Disorder, Dependent Personality Disorder, Obsessive-Compulsive Personality Disorder, Paranoid Personality Disorder, Schizotypal Personality Disorder, Schizoid Personality Disorder, Histrionic Personality Disorder, Narcissistic Personality Disorder, and Antisocial Personality Disorder. Test scores from the questionnaires will be thoroughly analyzed by [name] and his team followed by a more detailed discussion with the subject. Participants that display any characteristics of substance abuse or mental disorders will be excluded. The interview will also ascertain barriers to participation in the study, including participants' willingness to commit to the study, potential scheduling conflicts, support from household members to participate in the study, motivation and challenges facing the participant, details of the randomization and intervention, and other study-related issues of importance. This information will be used to identify and exclude from enrollment participants who will not be capable of completing the study. The results from the diagnostic interview will be used to provide an overall eligibility assessment for each candidate. A multidisciplinary team consisting of behavioral experts, dietitians, clinical staff, Medical Investigator ([name]), and study staff will discuss and approve a candidate for official admission to the study. If eligible, the participants will undergo a Pre-Randomization Visit, which will include a mandatory one-night test of ethanol consumption at the proposed dose to assess alcohol tolerance.

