#### Pre-Randomization Visit

Before enrollment in the study, all women will be required to undergo an overnight alcohol tolerance test at the required ethanol dose. Participants will receive the required ethanol dose at the pre-randomization visit along with instructions for consumption. Participants will be monitored via video chat technology (Skype) by study staff from the time the person starts drinking to 1-2 hours after they have finished drinking the alcohol. For minor adverse events experienced by the subject, such as headache, nausea, diarrhea or other similar issue, that are conveyed to the study staff, one should call the medical investigator. In the unlikely event that the person experiences serious adverse events and becomes agitated and destructive, or otherwise being out of control and a danger to herself and others, or if the person becomes so sedated that she is no longer responding to conversation in the audio portion of the Skype and is becoming unconscious, these would be indications to call 911. Women will be instructed to do a one-week alcohol-free washout. Women will be administered a dietary record and step log (pedometer provided) and asked to return these completed items at Clinic Visit 1. Pending adherence to the overnight alcohol test, the one-week ethanol-free washout, and the return of a dietary record, participants will undergo Clinic Visit 1.

#### Clinic Visit (CV) 1 and 2

At CV1 and 2, women will report to PBRC after an overnight fast during the luteal phase of the menstrual cycle. Anthropometric characteristics will be measured. Body composition scans (MRI, H-MRS, and FibroScan) and blood draws (Chem 26, insulin, testosterone (free and total)) will be performed. A sample of blood (serum and plasma) will be collected for archive. The appetite questionnaire will be administered. Participants will be randomized to the control or ethanol group and begin the dietary intervention.

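### Women removed after randomisation for repeated non-compliance have no CV2 arranged, so any removal restricts the outcome comparison by compliance

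*Protocol*

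**What the plan says.** The objective (section II) is "to test the effects of chronic ethanol consumption on adipose distribution and circulating testosterone during weight loss". Twelve women are to be enrolled, 7 to ethanol and 5 to control (section III, Subjects).

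Randomisation takes place at CV1: "Participants will be randomized to the control or ethanol group and begin the dietary intervention" (Clinic Visit 1 and 2). Compliance with study meals and alcohol is then followed for 8 weeks. A woman below 85% or above 100% is counselled, and beyond that "Repeated (i.e. >2 events) under- or over-compliance will result in the participant being dropped from the study" (Dietary and Alcohol Compliance). The section does not say whether an event is a meal, a dose, a day or a week.

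Table 1, Clinic Visit 1 and 2, and Study Procedures place MRI, 1H-MRS, FibroScan and free and total testosterone at CV1 and CV2 only. Both visits are in the luteal phase.

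Two steps before randomisation aim to limit later losses. On the screening interview the protocol says "This information will be used to identify and exclude from enrollment participants who will not be capable of completing the study". Entry to CV1 is conditional: "Pending adherence to the overnight alcohol test, the one-week ethanol-free washout, and the return of a dietary record".

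**The concern.** The rule is mandatory, acts on women already randomised, and ends participation in the study rather than participation in the feeding or drinking regimen. Because the outcomes named in the objective have a single post-baseline time point, a woman removed before week 8 contributes no change in any of them.

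Randomisation makes the two arms comparable as assigned. Once women are left out because of how they behaved under their assigned regimen, the arms compared at CV2 are partly formed by that behaviour. Compliance with an energy-restricted diet can plausibly be related to weight and fat loss, so this selection need not be harmless.

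This is a matter of data collection, which the protocol fixes. A SAP can choose analysis sets and missing-data methods, but it cannot supply a scan or blood sample that was never taken.

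**Working it through.** The protocol gives no sample-size calculation, event rate or expected dropout rate, so there is no figure of its own to reproduce beyond 7 + 5 = 12, which agrees. The check is mainly a reading of the sections side by side.

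1. **Timing.** Randomisation is at CV1 and compliance is scored in the 8 weeks that follow. Removal is therefore a post-randomisation event.

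2. **What is lost.** The outcomes in the objective are measured after baseline only at CV2. A removed woman also has no later weekly weights, no later weekly adverse-event and medication checks, and no week-8 pedometer collection. Weights recorded before removal remain, but they do not measure fat distribution or testosterone.

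3. **Whether any section restores CV2.**
   - Compensation sets payments for non-completers of $50 for CV1, $100 for the intervention and $100 for CV2. It is a payment schedule and arranges no visit.
   - Participant Safety provides telephone calls at 2 and 4 weeks after completion. These concern alcohol problems and collect no outcome.
   - The annual safety report covers reasons for dropout. It brings back no outcome data.

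4. **Share of an arm.** One ethanol removal: 1/7 = 0.143, or 14%. One control removal: 1/5 = 0.200, or 20%.

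5. **Precision compared with selection.** With equal standard deviations assumed, the standard error of a difference in means is proportional to √(1/n₁ + 1/n₂).
   - 7 v 5: √(1/7 + 1/5) = 0.586
   - 6 v 5: √(1/6 + 1/5) = 0.606, ratio 1.03
   - 7 v 4: √(1/7 + 1/4) = 0.627, ratio 1.07

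   One removal thus costs 3% to 7% in standard error. The loss of precision is small. The problem is that the missing woman is chosen by her compliance.

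6. **Arms.** In the ethanol arm, "Each bottle will contain a pre-measured dose of alcohol, and participants will drink one bottle per day of the week", and "the ingestion of all alcoholic drinks will be monitored by study staff via video technology", whereas only some meals are watched. Ethanol women therefore have one additional, video-monitored compliance item. Controls eat the same kind of provided meals and face the same limits. For them the protocol also requires: "Must be willing to abstain from alcohol for 8-weeks if randomized to non-alcohol control group". Extra food or drink is to be self-reported in both arms. The rule applies to both.

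**The case against.** This is a 12-woman pilot of controlled feeding, and an interest in women who actually followed the assigned regimen is defensible. Nothing is lost unless someone is removed. Screening for ability to complete, the tolerance test, the washout and counselling all make removal less likely. The separate CV2 payment suggests that attendance by a non-completer is not barred.

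Much of this stands. The harm is conditional, its probability is unknown, and the pilot setting limits what is at stake. But the precautions reduce the chance of removal without excluding it, and a payment line does not override an instruction to remove a woman from the study. An interest in compliers is not a reason to forgo CV2 either, because collecting the measurements does not dictate how they are used.

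A reader might infer more than the document supports:

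- **That the rule falls mainly on the ethanol arm, or exempts controls.** The compliance text covers meals and extra intake in both arms. The extra monitored item is a documented difference, but whether it would produce more removals cannot be told.
- **That only an analysis of compliers would remain.** An analysis of all randomised women is still possible from the CV1 values and the weights already recorded. It would rest on assumptions about the missing CV2 values that the data cannot test.
- **That the undefined event unit measures the damage.** It leaves the trigger unclear, but says nothing about the effect of a missing CV2.

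**Conclusion.** The concern holds as a conditional weakness in the plan that should be fixed. As written, the protocol removes randomised women from the study for repeated non-compliance and arranges no CV2 for them. If that happens even once, the comparison of the outcomes named in the objective is restricted by post-randomisation compliance.

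The only size that the document supports is the share of an arm lost per removal, 14% (ethanol) or 20% (control), assuming the planned 7 and 5 are reached. No removal rate, difference between arms, or direction or size of bias is claimed. The conclusion rests on reading the removal wording literally and on the absence of any section that schedules CV2 for a removed woman.

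**What to change.** Leave the compliance rule and all safety withdrawals as the investigators set them. Add to Dietary and Alcohol Compliance:

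*Removal under this rule ends the study intervention, not outcome collection; the woman is invited, if she agrees, to CV2 at its scheduled time (luteal phase, as for all participants), and removals are reported by arm and reason.*

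As a secondary wording point, state the unit of an event. The choice of main and sensitivity analysis sets stays with the SAP.

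The cost is a change of wording. CV2 is already planned for all 12 women, a separate CV2 payment is already listed, and reasons for dropout are already reported annually, so only the split by arm is new. The downside is that some removed women may decline, and those who attend may have returned to their usual diet and drinking, which would dilute a contrast of all randomised women. An analysis of compliers remains possible alongside it.

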#### Participant Safety

Subjects in the ethanol group will be closely monitored and frequently assessed throughout the study to identify any signs of alcoholism. A questionnaire (The Short Alcohol Dependence Data Questionnaire) will be administered weekly to evaluate the possibility of alcohol dependency. We will also re-administer the SASSI and MAST questionnaires. Study staff will verbally correspond with the participants weekly to assess any adverse events and ascertain any undesirable changes in mood or daily routine that may be associated with alcohol consumption. The Medical Investigator will have oversight through the duration of the study.

If any participant exhibits signs of alcohol dependency issues during the study based on self-report or the weekly questionnaires, a more comprehensive assessment (i.e. interview) by trained study staff and the medical investigator will be done. The subject will be withdrawn from the study and referred to a substance abuse center for treatment.

At the end of the intervention, participants will be contacted (phone) by trained study staff at 2 weeks and 4 weeks after completion of the study in order to assess if the women have acquired any alcohol abuse and/or dependency issues. If the subject exhibits any alcohol-related issues, she will be referred to a substance abuse center for treatment.

#### Study Procedures

Blood Draws: Blood will be collected at screening (Chem15, HCG), as well as at Clinic Visit 1 and Clinic Visit 2 (Chem26 + insulin, testosterone (free and total)). Blood (serum and plasma) will also be archived at the CV1 and CV2 time points.

Magnetic Resonance Imaging (MRI): scABD AT and VAT volumes will be defined and quantified with magnetic resonance imaging (MRI) using a 3.0T scanner (GE, Discovery 750w) by obtaining ~581 images from the dome of the liver to the pubic symphysis. Images will be analyzed by a single trained analyst.

H-Magnetic Resonance Spectroscopy (MRS): Intrahepatic lipid will be measured by H-MRS on a 3.0T whole body imaging and spectroscopy system (GE, Discovery 750w) with a commercially available H body coil. IHL content will be determined with jMRUI (Java-Based Magnetic Resonance User Interface), and IHL peak areas will be expressed relative to the peak area of an external phantom of known constant concentration (peanut oil signal).

FibroScan: Liver assessments will be obtained using a FibroScan ultrasound transient elastography device. The participant lies supine, a lubricating gel is applied to the skin at the level of the liver, and a hand-held probe is pressed against the gel as is done in a traditional liver ultrasound exam. Ultrasound images of the liver are obtained, guided by the FibroScan user interface. From these images, quantitative measurements of liver fat content and stiffness are obtained and uploaded to the study database. The procedure takes ~20 minutes.

The FibroScan procedure can identify clinically-significant levels of liver fibrosis and/or steatosis. A result deemed significant by the medical investigator of this study will trigger a clinically actionable incidental finding.

Radioimmunoassay (RIA): Testosterone levels will be measured by standard radioimmunoassay reagent sets.

Physical Activity: We will collect physical activity data with a pedometer to determine the number of steps per day.

Appetite Questionnaire: Retrospective Visual Analogue Scale (RVAS) will be used to measure average ratings of appetitive sensations that participants experienced over the past week (17,18). This validated method of collecting VAS data has been found to be consistent with daily assessments of satiety.

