#### **IV. EXPERIMENTAL DESIGN AND METHODS**

All study visits and clinic procedures will be conducted over the course of 1 year at Pennington Biomedical Research Center (PBRC) by trained nurses and research staff in accordance with standard operating and quality control procedures approved by PBRC's Institutional Review Board (IRB). This is a between-subjects parallel study design. All women will undergo a 30% energy restriction for 8-weeks and will be randomized to an ethanol-consuming group or a non-ethanol control group at the start of the study.

Table 1: Schedule of Study Events					
Tests	SV 1	Pre-Rand Visit	CV1	Intervention wk 1- wk 8	CV 2 (wk 8)
Informed Consent/Lifestyle Interview	X				
Height (SV1 only)/Metabolic Weight/BMI, Waist and Hip Circumference, Pulse, and Blood Pressure	X		X		X
Alcohol-related questionnaires (The Short Alcohol Dependence Data, SASSI, MAST)	X			X	
Pedometer Distributed/Collected		X		X (Wk8)	
Food Record/Washout Instructions		X			
Food Record Compliance Check			X		
Medical History/ Physical/ Medications	X				
Medications/Adverse Event Report			X	X(wkly)	X
Fasting Blood Draw*	X†		X*		X*
Questionnaires (retrospective VAS)			X		X
MRI,  H-MRS, FibroScan			X		X
Physical Activity (steps/day)			X		X
Alcohol Tolerance Test		X			
Randomization			X		
Controlled Feeding Dietary Intervention				X	
Body Weight				X	

CV, Clinic Visit; SASSI, Substance Abuse Subtle Screening Inventory; MAST, Michigan Alcoholism Screening Test; VAS, Visual Analogue Scale / †Chem 15, HCG / \*Chem 26, insulin, free and total testosterone and archives

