## **Study Visits**

### **Screening Visit 1 (S1)**

SV1 will be conducted the morning after a ~10-hr overnight fast. After acknowledging understanding of the study and all procedures, subjects will sign an informed consent. Demographics, vital signs, and medical history will be assessed. A physical exam will be administered. Anthropometric characteristics (i.e. height, metabolic weight, BMI, blood pressure, waist and hip circumference) will be measured. A blood sample will be collected for laboratory safety tests and menstrual cycle status will be determined.

A semi-standardized Lifestyle (diagnostic) Interview will be administered by trained behavioral staff (Master's Level Psychologists) and overseen by clinical psychologist and Co-Investigator [name]. The interviewer will investigate any current or lifetime prevalence of substance use and will identify and exclude for psychological co-morbidities that preclude participation in the study. Substance Abuse Subtle Screening Inventory (SASSI) and Michigan Alcoholism Screening Test (MAST) questionnaires will be administered. All

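### Pregnancy is an exclusion, but the only scheduled test is HCG at screening, with no repeat before randomisation or during eight weeks of daily ethanol

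*Protocol*

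**What the plan says.** Section III.c of the protocol lists pregnancy among the excluded conditions affecting metabolism or body weight: "i.e. uncontrolled thyroid conditions, bariatric surgery, pregnancy, breastfeeding". HCG is named in two places, both tied to screening: the SV1 footnote of Table 1 and the Blood Draws paragraph under Study Procedures, which reads "Blood will be collected at screening (Chem15, HCG), as well as at Clinic Visit 1 and Clinic Visit 2 (Chem26 + insulin, testosterone". The Table 1 footnote for CV1 and CV2 gives "Chem 26, insulin, free and total testosterone and archives", and the Clinic Visit 1 and 2 text gives the same tests. Neither mentions HCG.

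Between SV1 and CV1 comes the Pre-Randomization Visit, with a tolerance dose for every woman and then an abstinence period: "Women will be instructed to do a one-week alcohol-free washout". No upper limit is set on the interval. Randomisation and the diet start at CV1, and the ethanol group then takes one pre-measured 35 g bottle a day for eight weeks.

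The protocol does have indirect safeguards. Contraception must have a failure rate of "less than 1% per year, when used consistently and correctly". At SV1, "menstrual cycle status will be determined". CV1 and CV2 are timed to the luteal phase. Adverse events are checked weekly, and the safety monitoring plan describes monthly contact with the Medical Investigator or a designee.

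**The concern.** An exclusion is only as good as its last check. A pregnancy too early to show at SV1, or one begun afterwards, would come to light only indirectly while the study hands out ethanol every week. The possible harm is serious, the exposure is supplied by the study, and a schedule of safety tests belongs in the protocol rather than in an analysis plan.

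There is a smaller cost to the data. Pregnancy is excluded because it affects metabolism and body weight, and one woman is 1/7, or 14%, of the ethanol group. A pregnancy found after randomisation would also force a post-randomisation exclusion in a trial of 12.

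**Working it through.** **Scheduled pregnancy tests, visit by visit** (Table 1, visit descriptions, Blood Draws, safety monitoring plan):

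| Time | Pregnancy test |
|---|---|
| SV1 | HCG |
| Pre-Randomization Visit | none |
| CV1 (randomisation) | none |
| Weeks 1 to 8, weekly check-in | none |
| Monthly draw (safety plan only) | liver enzymes only |
| CV2 | none |

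The protocol gives no figure for this risk, so there is none to reproduce.

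**Chance of a conception during dosing.** The inputs are 7 women in the ethanol group (section III.a), 8 weeks (section IV) and a ceiling of 1% failure per year (section III.b).

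- Woman-years at risk: 7 × 8/52 = 1.08.
- P(at least one) = 1 − 0.99^(7 × 8/52) = 1 − 0.99^1.077 = 1.08%, about 1.1%.

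This treats every woman as being at the ceiling rate. Tubal ligation, abstinence and a vasectomised or same-sex partner are all permitted methods, so the real rate is probably lower.

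**Study dose against usual intake.**

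- Study dose: 2.5 × 7 = 17.5 drinks, or 35 × 7 = 245 g, a week.
- Eligibility floor ("typically consuming at least 8 drinks per week, but no more than 4 per day"): 8 × 14 = 112 g a week.
- Exclusion threshold (section III.c): 28 drinks, or 28 × 14 = 392 g, a week.
- Midpoint of 8 and 28: 18 drinks, so the study dose sits near the middle of the eligible range.

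**What a week-4 test can and cannot do.** Total study ethanol is 35 × 56 = 1,960 g, of which 35 × 28 = 980 g is dispensed after week 4. A positive test at week 4 would stop that second half. This is gross: it does not subtract what the woman would have drunk anyway, and it assumes that the pregnancy had not already been noticed. If HCG turns positive 1 to 2 weeks after conception (an assumption), a week-4 test can show conceptions from the first 3 to 2 of the eight weeks. At a constant rate that is 3/8 to 2/8, or 38% to 25%, of those in the dosing period. It would also show any conception too recent to be seen at CV1. The constant rate ignores cycle timing, so these shares are rough.

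**The case against.** The strongest reply is that the risk is small by the protocol's own terms and that several routes to detection exist. That largely stands. Contraception is required throughout, women are seen weekly, and luteal timing of CV1 and CV2 forces attention to cycles. A conception from an earlier cycle would usually mean no intervening period, which sits badly with placing the woman in the luteal phase. One in the current cycle may be too recent for HCG to show. A CV1 test would therefore find little, and no detection yield is claimed for it here. Its value is to verify the exclusion at the point of randomisation. The protocol does not say how the luteal phase is confirmed, and none of these safeguards is a pregnancy test.

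A reader might infer more than the documents support in four ways:

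- **That the protocol contradicts itself on HCG.** It does not: the places that list the blood tests agree.
- **That the study more than doubles these women's drinking.** That compares 17.5 drinks only with the floor of 8. For women in the upper part of the eligible range the study adds nothing or reduces intake.
- **That actual contraceptive failure is far above 1%.** The protocol's figure does assume consistent and correct use, but the documents give no other rate.
- **That the tolerance dose needs its own test**, because "all women will be required to undergo an overnight alcohol tolerance test at the required ethanol dose". This is a single dose of about 2.5 drinks in women who already drink daily or almost daily, followed by a week of abstinence. A separate test would add very little.

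**Conclusion.** The point holds as a weak design choice that is cheap to mend. Pregnancy status is checked once, at an unlimited distance from randomisation, and not again during eight weeks of study-supplied ethanol. The probability is low: about 1.1% for at least one conception among 7 women, resting on the 1% per year ceiling applied to all of them, and probably less in practice. The added alcohol exposure cannot be fixed from the documents, since usual intake may lie below or above the study dose. Most of the risk falls in the ethanol weeks, so a CV1 test alone would not cover it, and a single mid-course test would cover only part. No statistical figure in the protocol changes. The change should be made because the possible harm is serious and the remedy small.

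**What to change.** 1. Add HCG to the blood already drawn at CV1 for all women. Require a negative result before randomisation and before the pharmacist dispenses the first ethanol, so that a positive is a screening failure and not a post-randomisation exclusion.
2. Add one pregnancy test at about week 4 for the ethanol group, with dispensing stopped on a positive result. The monthly liver-enzyme draw in the safety monitoring plan can carry it if that draw is in fact performed; Table 1 and Blood Draws do not schedule it. Otherwise use a urine test at the weekly check-in.
3. Amend Table 1 and its footnote, the Clinic Visit 1 and 2 text and the Blood Draws paragraph to match.

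The cost is 12 + 7 = 19 assays and a short wait for the CV1 result. The protocol does not state a turnaround time, and randomisation and the diet start at CV1, so the site should confirm how long that wait would be.
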